5.0 Statistical Considerations

Data will be analyzed using IBM SPSS Version 22.0 (IMB Corps., Armonk, NY). Descriptive statistics will characterize the sample on demographic, clinical, safety, and feasibility metrics. We will compare safety and feasibility between groups using chi-square and *t*-tests for independent samples (*Specific Aim 1*). The efficacy of the intervention on study variables (*Specific Aim 2*) will be examined using a 2 (Group) by 2 (Time), mixed factor ANOVA. A completers analysis will be conducted (i.e., $\geq 75\%$ of sessions completed). Effect sizes associated with F-statistics will be expressed as eta-squared (η^2), and effect sizes based on mean differences will be expressed as Cohen's *d*.

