3.0 Enrollment/Randomization

National MS Society, , <http://nationalmssociety.org/for-professionals/researchers/index.aspx>

A convenience sample of 20 persons with progressive MS will be enrolled for this pilot clinical trial. Recruitment will occur through neurologists at the IU Health Neuroscience Center. Each participant will be given time to read the consent form or have it read to them and to ask questions (see Informed Consent Draft). Consent will be obtained before randomization and assessments. The consent process will take place at the Indiana Center for Advanced Neurorehabilitation (ICAN) in the Neurorehabilitation and Robotics IU Health Neuroscience Center, [name] [contact].

If found eligible for the study and agree to consent to participate, subjects will be matched based on disability level (EDSS), and randomized to either conventional physical therapy (CPT) group or CPT with G-EO training using a random numbers generator and concealed allocation.

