Following completion of day 1 assessments, all subjects will be scheduled for the intervention phase of the study. Regardless of group allocation, each participant will receive 20 total visits scheduled ideally for two times a week for 10 weeks. Following the completion of the first 10 treatments, all subjects will be asked to complete assessments #1 thru #3 above. Following completion of the additional 10 treatments (total of 20 treatment sessions), each subject will complete all assessments performed on Day 1. (See Table 1) If a subject cancels a treatment session, it will be rescheduled to ensure that all subjects complete the total of 20 treatment sessions prior to final testing. If a subject misses three consecutive treatment sessions, they will be dropped from the study due to inconsistency in treatment carryover. Cancellations and changes in patient scheduling represents a true clinical environment and represents normal clinical patient management. Therefore, the emphasis is on total number of treatments (20) and not on total number of weeks.

Table 1. Summary Clinical Trials (14-week span) Procedures with Human Subjects.

Pre-Intervention Phase		Intervention Phase	Mid Intervention Phase	Intervention Phase	Post Intervention
Day 1	Day 1 Measurement	6 weeks intervention period	Mid Treatment Assessment	6 weeks intervention period	Post Assessment

 • Screening of Inclusion • Informed consent obtained • Disability match and random assignment to CPT or GEO 	Outcome Measurement 
 1. Comfortable Walking Speed/Mechanics Trial 1 (14') 2. Trial 2 (14') 3. Trial 3 (14') 2. Walking Endurance 2 MWT 3. Balance Neurocom 4. Fatigue Modified Fatigue Impact Scale 5. Depression Hospital Anxiety and Depression Scale 6. Pain McGill Pain Questionnaire 7. Quality of Life MS Impact Scale 8. ADLs 	Treatment and control group 2x a week	Outcome Measurement 
 1. Comfortable Walking Speed/Mechanics Trial 1 (14') 2. Trial 2 (14') 3. Trial 3 (14') 2. Walking Endurance 2 MWT 3. Balance Neurocom 	Treatment and control group 2x a week	Outcome Measurement 
 1. Comfortable Walking Speed/Mechanics Trial 1 (14') 2. Trial 2 (14') 3. Trial 3 (14') 2. Walking Endurance 2 MWT 3. Balance Neurocom 4. Fatigue Modified Fatigue Impact Scale 5. Depression Hospital Anxiety and Depression Scale 6. Pain McGill Pain Questionnaire 7. Quality of Life MS Impact

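### The planned 2 × 2 ANOVA tests efficacy on unadjusted change scores; adjusting the final value for baseline and EDSS would usually give a tighter estimate from 20 participants at almost no cost

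*Combined protocol and SAP*

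**What the plan says.** Section 5.0 (Statistical Considerations) gives Aim 2 one model: efficacy "will be examined using a 2 (Group) by 2 (Time), mixed factor ANOVA". It names no covariate. On reporting, it states that "Effect sizes associated with F-statistics will be expressed as eta-squared" and that mean differences will be given as Cohen's d; no confidence interval is mentioned.

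Section 3.0 (Enrollment/Randomization) says that "subjects will be matched based on disability level (EDSS), and randomized to either conventional physical therapy (CPT) group or CPT with G-EO training". The size is set without a power calculation: "A convenience sample of 20 persons with progressive MS will be enrolled for this pilot clinical trial". No analysis in section 5.0 contains EDSS or a pair term.

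Section 4.0 (Study Procedures) takes every outcome on Day 1 and again after the last session. Gait, walking endurance and balance are also measured midway: "Following the completion of the first 10 treatments, all subjects will be asked to complete assessments #1 thru #3 above". Section 5.0 does not say which two times form the Time factor; baseline and final are assumed here.

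**The concern.** Twenty participants is a small sample, so an analysis should use the prognostic information already in hand. Two such items are available for everyone at entry: the baseline value of each outcome, and EDSS, which is both an eligibility criterion and the matching factor. The planned model uses baseline only by subtracting it, which fixes its coefficient at 1 whatever the data show, and it leaves EDSS out.

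What is at stake is the width of the interval around each treatment difference. The estimates and effect sizes are what a pilot hands on to later work. The validity of the comparison between randomised groups is not in question. The point concerns the model only; it says nothing about who is analysed, including the completers analysis in the same section.

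**Working it through.** **The plan's own figure.** There is none to reproduce: the documents give no alpha, power, effect size, SD or correlation.

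**Inputs.** From the documents: N = 20, two groups, matching on EDSS, two Time levels. Assumed: 10 pairs with one member per arm, equal SD (set to 1) at both times, pre–post correlation ρ = 0.5, 0.7, 0.85 or 0.9, EDSS–outcome correlation r = 0.5, complete data.

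**Step 1: what Group × Time tests.** With two times, the Group × Time F equals t² from a two-sample t-test on change, with 18 residual df. On one simulated data set the two agree: F = 7.869 and t² = 7.869.

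**Step 2: variances.**
- Change score: 2(1 − ρ).
- Final value given baseline and EDSS, when EDSS correlates r with the outcome at both times (so is unrelated to change): (1 − ρ)(1 + ρ − 2r²)/(1 − r²).
- Ratio of the second to the first: (1 + ρ − 2r²)/[2(1 − r²)], which is (ρ + 0.5)/1.5 at r = 0.5.
- If EDSS acts only through baseline, the residual variance is 1 − ρ² and the ratio is (1 + ρ)/2.

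**Step 3: small-sample price.** ANCOVA with two covariates has 16 df, so the critical t rises from 2.101 to 2.120 (factor 1.009). Chance imbalance in baseline multiplies the variance by about 17/16; matching largely removes the corresponding term for EDSS. Hence

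width ratio (ANCOVA / planned) ≈ √(variance ratio × 17/16) × 1.009.

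**Step 4: EDSS unrelated to change.**

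| ρ | Variance ratio | Width ratio, formula | Width ratio, simulated | Planned interval wider by |
|---|---|---|---|---|
| 0.5 | 0.667 | 0.849 | 0.849 | 18% |
| 0.7 | 0.800 | 0.930 | 0.930 | 8% |
| 0.85 | 0.900 | 0.987 | 0.986 | 1% |
| 0.9 | 0.933 | 1.005 | 1.005 | no gain |

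The last column is 1/ratio − 1, for example 1/0.849 = 1.178. The simulation used 40,000 trials per setting.

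**Step 5: EDSS acts only through baseline.**

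| ρ | Variance ratio (1 + ρ)/2 | Width ratio, formula | Planned interval wider by |
|---|---|---|---|
| 0.5 | 0.750 | 0.901 | 11% |
| 0.7 | 0.850 | 0.959 | 4% |
| 0.85 | 0.925 | 1.000 | no gain |
| 0.9 | 0.950 | 1.014 | no gain (ANCOVA 1.4% wider) |

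Simulation gives 0.900, 0.958, 1.000 and 1.014. Here baseline alone does slightly better (0.888, 0.945, 0.986, 1.000), so the EDSS term costs about 1.4% of width.

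**Step 6: EDSS predicts change by ±0.3 SD per SD.** The change variance becomes 2(1 − ρ) + 0.3² = 2(1 − ρ) + 0.09; the residual variance given baseline and EDSS does not move. Because the slope enters squared, its sign does not matter for this comparison. Simulated width ratios for a positive slope are 0.811, 0.864, 0.859 and 0.827; over both directions they lie between 0.81 and 0.87. The planned interval is therefore 1/0.87 − 1 = 15% to 1/0.811 − 1 = 23% wider.

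The sign does matter for where the gain comes from. Adjusting for baseline alone gives 0.97, 1.01, 1.03 and 1.02 if the slope has the same sign as the EDSS–outcome correlation, but 0.80, 0.86, 0.90 and 0.91 if the signs are opposite.

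**Step 7: validity.** With no treatment effect and EDSS unrelated to change, Group × Time rejected in 5.0–5.2% of simulated trials at nominal 5%. With a positive slope of 0.3 it rejected in 2.2–4.2%, which is conservative. Ignoring the matching does not inflate the error rate.

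**The case against.** **No error is shown.** Change-score analysis and ANCOVA are both valid here, and no stated figure in the plan is wrong. This is a pilot with a convenience sample and no power target to miss. That stands, and it sets the severity.

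**Every magnitude is assumed.** Eligibility spans EDSS 4.0–7.5, and wide variation between people would tend to push ρ for mobility outcomes towards the region where the gain vanishes. This also stands: the result runs from 23% wider to about 1% narrower. The simulations also assume 20 complete participants in intact pairs, which dropouts would disturb.

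**EDSS need not earn its place.** If it carries nothing beyond baseline, including it costs about 1.4% of width. A reader might infer from the 15–23% case that EDSS supplies the gain. That does not hold: with an opposite-signed slope, baseline alone captures most or all of it. The documents do not say which case applies. The case for including EDSS is that the design matched on it, that it may help appreciably, and that it costs little when it does not.

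**The F-test is not named.** A reader might also infer that, because section 5.0 does not say which F carries efficacy, the trial could judge it from the Group main effect, which averages in the pre-treatment value. The documents do not support that. In a two-arm trial with a Group by Time model, the interaction is the natural efficacy test, and nothing points to another. The silence is a missing detail that one clause settles.

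**Conclusion.** The point holds as a matter of precision. The efficacy test in section 5.0 amounts to an unadjusted comparison of change scores, and for ρ up to about 0.7 a baseline- and EDSS-adjusted ANCOVA gives a narrower interval in every scenario examined. The planned interval is 4–18% wider at ρ of 0.5 to 0.7 when EDSS does not itself predict change. It is about 15–23% wider across ρ from 0.5 to 0.9 when EDSS predicts change by 0.3 SD per SD. At ρ of 0.85 to 0.9 there is little or no gain unless EDSS predicts change.

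These sizes rest on 10 EDSS-matched pairs, r = 0.5, equal SDs and complete data, none of which the documents give. The finding is not one of bias or of an invalid test, and it does not show that the trial is underpowered. It is a low-severity, nearly free improvement.

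**What to change.** Put in section 5.0:

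> For each Aim 2 outcome, the efficacy estimate is the group difference at the final assessment, with 95% CI, from ANCOVA adjusted for that outcome's baseline value and EDSS. The Group × Time F of the 2 by 2 ANOVA, with its eta-squared, is a sensitivity analysis.

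This also settles which F and which time point are meant, and adds an interval that the section lacks. It does not alter who is analysed.

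**Cost.** Wording only; baseline outcomes and EDSS are already obtained. Two residual degrees of freedom are spent (18 to 16). For ρ from 0.5 to 0.9 with matching, the ANCOVA interval is at worst about 1.4% wider. As ρ approaches 1, the formula above tends to √(17/16) × 1.009 = 1.040.

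If the matching achieved no balance, the simulated worst case is about 3% (ρ = 0.9, r = 0.5, EDSS unrelated to change). If EDSS then also adds nothing beyond baseline, replacing 17/16 by 17/15 for two unbalanced covariates gives √(0.95 × 17/15) × 1.009 = 1.047, under 5%.

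Use EDSS as a single linear covariate. A full pair term would leave only 9 df: a paired analysis of change had lower power than Group × Time in every setting run.

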4.0 Study Procedures

Screening

Potential subjects will be referred to the study via IU Health Physicians who specialize in the treatment and management of individuals with Multiple Sclerosis. A member of the research team will screen the referral by contacting the physician and confirming they meet the necessary inclusion and exclusion criteria. Following confirmation of criteria, potential subjects will be contacted by phone to schedule an initial visit for consent and assessment of baseline data.

Assessments

The study outcomes will be collected by treatment-blinded researchers. All participants on Day 1 who consent to be in the study will complete the following mobility outcomes:

1. Spatial and temporal gait kinematics will be assessed using a PKMAS Zeno Walkway (Protokinetics). Participants will be asked to walk over a 14 foot pressure mat that will capture their gait kinematics and speed.
2. A 2-minute walk (2MWT) tests to determine walking endurance. Subjects will be asked to walk for 2 minutes along a 30m track. Subjects may stop and rest as often as needed.
3. Balance assessment using the Neurocom Balance Master. Subjects will be asked to stand on a balance platform while the load cells in the force-plate measures postural stability when challenged. All subjects will be in a safety harness to prevent falling.
4. Their level of perceived fatigue using the Modified Fatigue Impact Scale. They will complete a questionnaire.
5. Their level of depression using the Hospital Anxiety and Depression Scale. They will complete a questionnaire.
6. Their level of pain assessed by the McGill Pain Questionnaire. They will complete a questionnaire.
7. Their level of health-related quality of life assessed by the Multiple Sclerosis Impact Scale-29. They will complete a questionnaire.
8. Their perceived ability to perform Activities of Daily Living (ADL) using the Late-Life Function and Disability Inventory. They will complete a questionnaire.

Participants who complete the first 6 weeks of training will be asked to complete assessments 1 thru 3. Participants who complete all 12 weeks of training will be asked to complete all assessments one final time.

Schedule

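### Gait, 2MWT and balance are measured three times, but the only efficacy model has two time levels, so no analysis is specified for the mid-treatment values

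*Combined protocol and SAP*

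**What the plan says.** Section 4.0, Assessments, lists eight outcomes for Day 1: "All participants on Day 1 who consent to be in the study will complete the following mobility outcomes". Assessments 1-3 are walkway gait, the 2-minute walk and Neurocom balance; 4-8 are questionnaires. At mid-treatment only 1-3 are repeated. Assessments sets this by weeks ("Participants who complete the first 6 weeks of training will be asked to complete assessments 1 thru 3") and Schedule sets it by sessions ("Following the completion of the first 10 treatments, all subjects will be asked to complete assessments #1 thru #3 above"). After session 20, "each subject will complete all assessments performed on Day 1". Table 1 shows the same three occasions for 1-3 and two for 4-8. The week-based and session-based timings of the mid test are a separate matter and need to be reconciled.

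Section 5.0 says the study variables for Aim 2 "will be examined using a 2 (Group) by 2 (Time), mixed factor ANOVA". It does not say which two times are meant. The rest of the section covers three things:

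- Sample description: "Descriptive statistics will characterize the sample on demographic, clinical, safety, and feasibility metrics".
- Aim 1: "We will compare safety and feasibility between groups using chi-square and" t-tests.
- A restriction by attendance: "A completers analysis will be conducted", defined as at least 75% of sessions.

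None of these mentions the mid-treatment test.

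**The concern.** Mobility is the first domain named in Specific Aim 2, and assessments 1-3 are the only outcomes the trial pays to measure a third time. A two-level Time factor cannot hold three occasions, so one of them has no stated role.

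Two things are at stake:

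- **Time course.** As written, the plan yields no estimate of whether a group difference appears in the first or the second block of ten sessions.
- **Partial data.** Section 4.0 drops anyone who misses three consecutive sessions, and final testing follows session 20. Someone who leaves after the mid test has a blinded post-baseline result on file, but a Day 1-to-post ANOVA needs both values and omits that person. With 20 participants, each one is 5% of the sample (1/20).

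**Working it through.** The plan states no alpha, SD, effect size, power or dropout rate, and the sample of 20 is a convenience sample. There is no figure of the plan's own to reproduce.

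**1. Occasions against time levels** (Section 4.0 and Table 1 against Section 5.0)

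| Outcomes | Occasions | Time levels in model | Values with no stated analysis (N = 20, complete data) |
|---|---|---|---|
| Assessments 1-3 | 3 | 2 | 60 - 40 = 20 per outcome |
| Assessments 4-8 | 2 | 2 | 0 |

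**2. Full retention.** The Day 1-to-post group contrast uses only those two values and is valid without the mid value. A three-level omnibus interaction test would not reliably help. Assume 10 per arm, two-sided 5%, within-person correlation 0.7 and a post-treatment difference of 0.8 SD. The noncentrality is (n/2) × Σ(m − mean m)² / (1 − correlation), where m is the group difference at each visit.

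- Two times (0, 0.8): 5 × 0.32 / 0.3 = 5.33 on F(1,18); power 0.59.
- Three times, linear growth (0, 0.4, 0.8): 5 × 0.32 / 0.3 = 5.33 on F(2,36); power 0.50.
- Three times, full effect by mid (0, 0.8, 0.8): 5 × 0.427 / 0.3 = 7.11 on F(2,36); power 0.62.

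**3. Dropout in one arm only.** Assume 10 per arm, no true effect, and 2 of 10 leaving one arm after the mid test. Let M and P be the changes from Day 1 to mid and to post, each with SD 1, and let r be their correlation. Suppose the two with the worst M leave. The two lowest of ten standard normal values average -1.539 and -1.001, so the other eight average (1.539 + 1.001)/8 = 0.318. Their mean P is then r × 0.318, against 0 in the other arm.

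| r | Leaving decided by M alone | Leaving mostly driven by M (simulation) |
|---|---|---|
| 0.5 | 0.16 | 0.13 |
| 0.7 | 0.22 | 0.18 |
| 0.85 | 0.27 | 0.22 |

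The range is about 0.12 to 0.27 SD of change, in favour of the arm that loses people. The lower end depends on how loosely leaving follows M. If noise with the same SD as M is added to the ranking, the bias is 0.318r/√2, which is 0.11 at r = 0.5; with a looser link it is 0.10 at r = 0.7. The SE of the contrast is about 0.46, so the largest bias is 0.27/0.46 = 0.6 SE. A likelihood-type regression estimate that uses M brings the bias to within 0.01, with an SE within about 2% of the completers' SE.

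**4. Equal dropout in both arms.** If 2 of 10 leave each arm by the same mechanism, both means shift by the same amount and the bias cancels. What remains is precision: using M cuts the variance of the post contrast by about 2% to 10%, more at higher r.

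**5. Covariance structure.** Under compound symmetry with visit variance σ² and correlation c, each change has variance 2σ²(1 − c), and the two changes have covariance σ²(1 − c). The correlation between M and P is therefore forced to 0.5. Where the true r is 0.7 to 0.85, the scenario in step 3 leaves about 0.05 to 0.11 SD of bias. An unstructured matrix imposes no such constraint.

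**6. Completers rule.** 75% of 20 sessions is 15. Someone who leaves with 10 to 14 sessions done is outside the completers set whatever the model. Someone who leaves with 15 to 19 is inside it but has no scheduled post test, so the mid test is that person's only post-baseline mobility result.

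**The case against.** Taking an intermediate measurement while testing Day 1 to post is a legitimate design, and this is a pilot with a convenience sample. Cancelled sessions are rescheduled so that everyone reaches 20, the removal rule applies to both arms alike, and nothing in the documents links leaving to poor mobility. The bias needs one-sided dropout that follows mid-treatment change, and even its largest value is below one SE. A three-level omnibus test can also lose power. All of this stands. It makes the point an inexpensive improvement and leaves the planned comparison sound under full retention. The power argument does not touch a model in which the single Day 1-to-post contrast is named.

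Two stronger readings are tempting, and the documents support neither:

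- A reader might infer that the mid-treatment data will be discarded. Section 5.0 does not say so; it specifies no analysis for them.
- A reader might infer that, because the two levels are unnamed, the sponsor could pick any of three pairings of visits and so inflate the false-positive rate. One model is applied to all study variables, and assessments 4-8 have only Day 1 and post, so Day 1 to post is the natural reading. Naming the levels closes the question.

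**Conclusion.** The mismatch is certain: three occasions for assessments 1-3, two time levels in the only efficacy model, and no stated use for the mid value. Its consequence is modest and conditional. With full retention nothing is lost for the Day 1-to-post contrast, and only the time course goes unreported. With equal dropout of 2 of 10 per arm, the loss is about 2% to 10% of variance. Bias of about 0.12 to 0.27 SD of change arises only if 2 of 10 leave one arm, none leave the other, and leaving follows poor mid-treatment change. A reader might conclude that the efficacy comparison is biased. The documents do not support that: they give no dropout rate, no difference by arm and no link between leaving and outcome. The bias figures also assume 10 per arm, normal changes, no true effect and r between 0.5 and 0.85.

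**What to change.** In Section 5.0:

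- For assessments 1-3, replace the 2 × 2 ANOVA with a linear mixed model (SPSS MIXED) containing Group, Time (Day 1, mid, post) and their interaction. Use unstructured covariance and small-sample degrees of freedom, on every available visit of all randomised participants.
- Name the single-df Day 1-to-post group contrast, not the omnibus interaction, as the efficacy contrast, and Day 1-to-mid as secondary.
- State that the completers analysis (at least 75% of sessions) is separate and supporting.
- For assessments 4-8, keep two time levels and name them as Day 1 and post.

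The cost is a few sentences and a different procedure in the same software, with no new visit, test or participant. The downside is that an unstructured matrix has 3 × 4/2 = 6 parameters for three visits against 2 × 3/2 = 3 for two, estimated from 20 participants.

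### Participants dropped from the study have no planned final assessment and no analysis set is stated for the 2x2 ANOVA, so a Day 1-to-post comparison can use only those who finish training

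*Combined protocol and SAP*

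**What the plan says.** Section 5.0 says that efficacy "will be examined using a 2 (Group) by 2 (Time), mixed factor ANOVA". It does not say which two of the three assessment occasions form the Time factor, who is included, or what happens when a value is missing. It then adds "A completers analysis will be conducted", with completers defined by attendance at 75% or more of sessions, and does not say whether this is the main analysis or an extra one.

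Section 4.0 decides who has data to analyse:

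- **Final visit.** Under Schedule: "Following completion of the additional 10 treatments (total of 20 treatment sessions), each subject will complete all assessments performed on Day 1". Under Assessments, the final visit is for those who complete all 12 weeks.
- **Cancelled sessions.** A cancelled session is made up: "it will be rescheduled to ensure that all subjects complete the total of 20 treatment sessions prior to final testing".
- **Removal.** "If a subject misses three consecutive treatment sessions, they will be dropped from the study due to inconsistency in treatment carryover". No assessment at or after removal is described.
- **Mid visit.** "Following the completion of the first 10 treatments, all subjects will be asked to complete assessments #1 thru #3 above". Assessments 4 to 8, the questionnaires, are taken only on Day 1 and at the end.
- **Length of training.** Under Schedule, "each participant will receive 20 total visits scheduled ideally for two times a week for 10 weeks". Assessments, Intervention and Table 1 instead describe 12 weeks, Table 1 as two six-week periods.

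**The concern.** A mixed ANOVA on two occasions needs both values from each participant. If the second occasion is the final visit, anyone removed earlier drops out of the comparison whatever analysis set is later declared, because the outcome was never sought. Randomisation then no longer protects the comparison: if removals differ between arms and are related to how participants were doing, the Group x Time estimate is biased. An analysis set can be clarified after the event, but an outcome that was never measured cannot be recovered.

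This matters because Aim 2 is worded as determining efficacy, and Section 5.0 will report F-statistics, eta-squared and Cohen's d. With 20 participants, each loss carries weight.

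**Working it through.** The plan has no figure of its own to reproduce: it gives no dropout rate, alpha, power or SD.

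**Step 1. Set the completer cut against the final visit.** Under the Schedule text, 0.75 x 20 = 15 sessions, while final testing follows 20 of 20.

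- Everyone with a final assessment has attended 20/20 = 100%, so the 75% cut excludes nobody who has final data.
- A participant who stops at 15 to 19 sessions meets the completer definition but has no planned final outcome.

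On the 12-week text, twice weekly implies 12 x 2 = 24 sessions (derived, not stated), and the cut becomes 0.75 x 24 = 18. The denominator therefore depends on which schedule text applies.

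**Step 2. See what the mid visit can supply.** A participant dropped before it has no post-baseline value for any outcome. One dropped after it has a mid value for outcomes 1-3 and none for outcomes 4-8.

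**Step 3. Size of the bias.** Assumptions: 1:1 allocation (10 per arm), standard normal change scores, no true effect, two-sided alpha 5%. In an arm that loses k participants, those lost are the k lowest on a latent variable correlated rho with the outcome. The test is a two-sample t-test on change, equivalent to the Group x Time F for two occasions.

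With losses in one arm only, bias = rho x S_k / (10 - k), where S_k is the sum of the k largest expected normal order statistics for n = 10 (1.539, 1.001, 0.656):

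- k = 1: 1.539 / 9 = 0.171 x rho
- k = 2: (1.539 + 1.001) / 8 = 0.318 x rho
- k = 3: (1.539 + 1.001 + 0.656) / 7 = 3.196 / 7 = 0.457 x rho

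Simulation with 200,000 trials per cell agrees and gives the type I error (ranges allow for simulation error):

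| rho | Bias in SD, k = 1, 2, 3 | Type I error, k = 1 to 3 |
|---|---|---|
| 0 | 0, 0, 0 | about 5% |
| 0.3 | 0.05, 0.09, 0.14 | 5.2-5.9% |
| 0.5 | 0.09, 0.16, 0.23 | 5.5-7.6% |
| 1.0 | 0.17, 0.32, 0.46 | 7.4-17% |

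For losses of 3 v 1, the bias is (0.457 - 0.171) x rho = 0.286 x rho: 0.09, 0.14 and 0.29 SD at rho 0.3, 0.5 and 1.0. For equal losses (1 v 1 to 3 v 3) it is zero. Type I error then stays at 5.2-5.8% for rho 0.3-0.5 but reaches 7.4-10.6% at rho 1.0.

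**Step 4. Modelling or collecting the data.** With visit correlations assumed at 0.80, 0.80 and 0.75, and 1, 2 or 3 lost from one arm (30,000 trials):

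| Situation | Bias in SD |
|---|---|
| Dropout after mid, driven by observed Day 1-to-mid change: finishers only | 0.09, 0.18, 0.26 |
| Same, likelihood model using mid data | 0.00 |
| Dropout driven by Day 1-to-post change: finishers only | 0.17, 0.32, 0.45 |
| Same, likelihood model using mid data | 0.12, 0.22, 0.31 |
| Same, dropped before mid, likelihood model | 0.15, 0.28, 0.40 |
| All post values collected | 0.00 |

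The model helps fully only when dropout depends on observed data. Collecting the final assessment removes the bias in every case.

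**The case against.** This is a 20-person convenience-sample pilot whose first aim is safety and feasibility, and a clearly labelled completers estimate is a defensible pilot summary. The arms are designed to match on contact, frequency and total time, so the documents give no particular reason to expect unequal losses. The emphasis on sessions is deliberate: "Therefore, the emphasis is on total number of treatments (20) and not on total number of weeks". The size rests wholly on assumptions. The standard error of a 10 v 10 difference is sqrt(2/10) = 0.45 SD, so a bias of 0.05-0.23 SD is about 0.1-0.5 standard errors. The 17% figure needs three losses from one arm, exactly the three worst responders. All of this stands and limits the severity. It does not supply a final outcome for anyone dropped.

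Three stronger readings are tempting, but the documents do not support them:

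- **That completers are the main or only Aim 2 analysis.** Section 5.0 does not say so, and the set may be supplementary. The gap is the same either way, since no wider set would have final data.
- **That the 75% cut would discard people with final data.** On a 24-session calendar one could attend as few as 8 sessions without three consecutive misses, and so perhaps be assessed but fall below 18. This applies the removal rule from the Schedule text to the 12-week text, ignores the Schedule text's rescheduling to 20 sessions, and treats someone at one third of sessions as having completed 12 weeks.
- **That attrition would go unreported.** Feasibility and Safety in Section 4.0 already plans retention and adherence rates, and Section 5.0 compares feasibility between groups.

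**Conclusion.** The point holds and should be fixed. Confidence is high on the text: no final assessment is planned for those dropped, and no analysis set, Time levels or missing-data method is stated for the ANOVA. The consequence is conditional. There is no bias if nobody is removed, if removal is unrelated to outcome, or, with no true effect, if both arms lose equally by the same mechanism. Under the assumptions above, losing 1-3 from one arm biases the estimate by 0.05-0.23 SD at correlations of 0.3-0.5, with type I error up to 7.6%. The effect is modest unless losses are both unequal and strongly related to outcome. A reader should not infer that the trial's result will be biased, only that the plan leaves it unprotected where protection is cheap.

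**What to change.** **Section 4.0.** Separate stopping training from leaving the study. Seek the mid and post assessments already in the schedule from every randomised participant who does not withdraw consent. For those who stop training, set these at calendar dates from Day 1, consistent with the reconciled schedule. The treatment-stopping rule stays with the investigators. Reconcile the 75% threshold, the 20-session requirement and the 10- and 12-week descriptions.

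**Section 5.0.**

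- Name Day 1 and post as the Time levels.
- Make the main Aim 2 analysis all randomised participants in their assigned group. Keep the completers analysis as supportive, with its session denominator stated.
- For post values still missing on outcomes 1-3, fit a likelihood-based repeated-measures model to Day 1, mid and post, with a simple covariance structure.
- For outcomes 4-8, analyse the available Day 1 and post data by assigned group, and add a sensitivity analysis over a stated range for the missing changes. For example, if 2 of 10 are missing and assumed 0.5-1.5 SD worse than those observed, the arm mean moves by 0.2 x 0.5 = 0.10 to 0.2 x 1.5 = 0.30 SD.
- Add to the planned retention reporting the reasons for missing final assessments and the weeks from Day 1 to each assessment, by arm.

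**Cost.** Wording changes and a few recall visits, some of which will be refused. The estimate is diluted by those who stop: if 2 of 10 stop and keep half the benefit (an assumption), it is 0.8 + 0.2 x 0.5 = 0.90 of the full-training effect. Assessment timing will differ between those who stop and those who continue, and should be reported.
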